#### 3.2 Secondary Outcome Measures

Basophil count, IL-1 $\beta$ , IL-8, exercise ventilation ( $\dot{V}_E$ ), tidal volume (VT), breathing frequency ( $f_B$ ), carbon dioxide production ( $\dot{V}CO_2$ )

#### 4.0 Eligibility Criteria

#### 4.1 Inclusion Criteria

- Men and women
- 18-35 years old
- Current collegiate or professional swimmer
- Currently training at least 300 minutes per week
- Self-reported to be healthy

#### 4.2 Exclusion Criteria

- Not within defined age range
- Current diagnosis of or using medication for:
  - Severe allergies
  - o Asthma
  - Exercise-induced asthma
  - Exercise-induced bronchoconstriction
- Pulmonary function test considered to be abnormal (defined as forced vital capacity (FVC) <80% of predicted, forced expiratory volume in one second (FEV1) <80% predicted, and/or FEV1/FVC ratio >5% of the predicted ratio)
- Hypertension during screening (systolic blood pressure >139 or diastolic blood pressure >89)
- Current tobacco or electronic cigarette use or consistent use within the last 2 years
- A contraindication for use of cetirizine HCI:
  - $\circ\,$  Previous adverse reaction to cetirizine HCl or a similar medication
  - Allergy to the food additives E218 or E216
  - An intolerance to or inability to absorb some sugars, such as lactose or sorbitol
  - Liver or kidney failure
  - Epilepsy or similar condition
  - A condition that makes urinating difficult
  - o Use of midodrine or ritonavir
- Are pregnant or could possibly be pregnant by self-report
- Subjects with current, irregular menstrual cycles (amenorrhea) or who had irregular menstruation patterns for greater than one year
- People who answer 'yes' to any of the pre-participation screening questions on page one of the PAR-Q+ questionnaire.

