#### 6.0 Enrollment/Randomization

We plan to recruit up to 30 participants for this project to ensure that at least 24 participants will complete the first two visits of the study.

Participants will be recruited from the Indiana University varsity swim team and the associated professional training group. Indiana University is home to a NCAA Division I swim team that is perennially among the nation's top-10 for both men and women. Participants will be recruited from this group of over 50 swimmers using a standard email script.

[figure not shown]
Potential participants will be given the basic information about the study and schedule an appointment for screening if they indicate that they would be interested in participating. Participants will be provided a with detailed description of study procedures prior to study enrollment. Participants will be asked to read the consent form at this time and be encouraged to ask any questions. Participants can then: 1) sign the consent form; 2) take it home for further consideration; or 3) decide not to participate. Participants will be screened once written informed consent has been given.

Experimental trials 3 and 4 will be completed in a double-blinded randomized crossover design. The randomization order will be determined using a customized program (Excel; Microsoft Corporation, Redmond, WA, USA). Subjects will be randomized using the randomization list by order of enrollment in the study by a researcher listed on the IRB personnel. This researcher will also be responsible for drug administration but will otherwise not participate in any data collection or analyses.

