## Figure 2: Photo of the Counsilman-Billingsley Aquatics Center where Visit 2 will take place.

Visits 3 and 4 will take place in the swim flume (Endless Pool). This pool works like a "swimming treadmill," pushing water from the front (near side in Figure 4) to the back at various flow rates to simulate various swimming speeds. A standard pulley is affixed to the back of the flume to add a tethered load to the swimmer, like changing the "grade" on a treadmill. This is a familiar training environment for high-level competitive swimmers. A photo depicting the swim flume in the IUB School of Public Health is below (Figure 4).

Figure 3: Photo of the swim flume where Visits 3 and 4 will take place.

- Height: Body height will be measured using a stadiometer.
- Weight: Weight will be measured using a scale.
- Heart rate: Resting heart rate will be obtained by taking a radial pulse for 15 seconds during the screening procedure. Exercising and pre-exercise heart rate will be continuously recorded using a specialized waterproof swimming heart rate monitor (Cardio Swim HR monitor; Freelap, Switzerland).
- Urine specific gravity: Urine specific gravity will be measured via refractometry.
- Blood pressure: Blood pressure will be measured using standard brachial artery manual auscultation techniques.
- Health history questionnaire: Participants will complete a health history questionnaire to ensure they meet the inclusion and exclusion criteria.

- Health history update questionnaire: Upon each visit to the laboratory participants will complete the heath history update questionnaire to ensure no changes in their health history has occurred.
- Pulmonary function: Pulmonary function will be examined using procedures described by the American Thoracic Society. Following 10 min seated rest, participants will be fitted with a previously disinfected non-rebreathing mouthpiece. Following 30 s of normal breathing the participants will be instructed to take a maximal inhalation followed by a maximal forced exhalation. This very large, very fast breath will be repeated three times. From this test peak expiratory flow rate (PEFR), forced vital capacity (FVC), forced expiratory volume in one second (FEV1), and the maximal expiratory flow at 50% vital capacity (MEF50) will be measured. These tests will be used to determine if the participants classify as having normal pulmonary function (Barreiro and Perillo, 2004).

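### The FEV1/FVC part of the spirometry exclusion (section 4.2) is wrong as written: its inequality runs opposite to the two limits beside it, and the direction and unit of the 5% are not stated

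*Combined protocol and SAP*

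**What the plan says.** Section 4.2 (Exclusion Criteria) lists "Pulmonary function test considered to be abnormal" as a reason for exclusion and defines it by three limits joined by and/or, so meeting any one excludes:

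- "forced vital capacity (FVC) <80% of predicted"
- "forced expiratory volume in one second (FEV1) <80% predicted"
- "FEV1/FVC ratio >5% of the predicted ratio"

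Section 7.0 (Study Procedures, Pulmonary function) describes the manoeuvre and says: "These tests will be used to determine if the participants classify as having normal pulmonary function". It gives no numerical limit for the ratio. The calendar in section 8.0 places spirometry at Visit 1 and again at Visits 3 and 4, but no section attaches a separate acceptance rule to the later measurements. Section 4.2 is therefore the only place where the ratio limit is set, and nothing elsewhere corrects it.

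**The concern.** The first two limits exclude low values. The third uses a greater-than sign, and no word says that the ratio must fall below, or differ from, the predicted one. A screener who applies the sentence as printed would not exclude a swimmer because the ratio is low, although a low ratio is what the other two limits can miss: FEV1 and FVC can each be at or above 80% of predicted while their quotient is well under its predicted value.

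Three things are at stake.

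- **Aim 1.** Under Hypothesis 1 in section 12.0, a fall in SpO2 of 5% or more in a single participant confirms the hypothesis. Section 1.0 names inadequate hyperpnea and ventilation-perfusion mismatch among the mechanisms of exercise-induced arterial hypoxemia. Airflow obstruction could plausibly act through these, so a desaturation in an obstructed swimmer would be hard to interpret.
- **Aim 3.** The correlation between desaturation and histamine release uses a pooled cohort given as n=12, where one or two people who desaturate for another reason can carry weight.
- **Screening.** Participants swim to exhaustion in the graded test (section 7.0), so an unclear respiratory screen also matters before testing starts.

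**Working it through.** No sample size, power or alpha figure depends on this limit, so there is no planned figure to reproduce. The check is to apply each possible reading of the sentence.

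**Inputs.** The three limits come from section 4.2. The documents give no predicted ratio, so I assume 0.80, 0.85 and 0.90.

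**Cut-offs on the observed ratio**

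| Reading | Formula | 0.80 | 0.85 | 0.90 |
|---|---|---|---|---|
| A. Exclude if above 5% of predicted | 0.05 × predicted | 0.040 | 0.0425 | 0.045 |
| B. Exclude if more than 5% above predicted, relative | 1.05 × predicted | 0.84 | 0.8925 | 0.945 |
| B. Same, percentage points | predicted + 0.05 | 0.85 | 0.90 | 0.95 |
| C. Exclude if more than 5% below predicted (word supplied), relative | 0.95 × predicted | 0.76 | 0.8075 | 0.855 |
| C. Same, percentage points | predicted − 0.05 | 0.75 | 0.80 | 0.85 |

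A fourth reading, D, supplies *differs from* and excludes on both sides of predicted.

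**Illustrative swimmers (assumed values).** The ratio as a percentage of predicted is approximated by FEV1 % predicted ÷ FVC % predicted. B, C and D are applied with 5% taken as relative.

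| FVC % | FEV1 % | Ratio, % of predicted | FVC or FEV1 limit met? | A | B | C | D |
|---|---|---|---|---|---|---|---|
| 100 | 100 | 100/100 = 100.0 | no | out | in | in | in |
| 110 | 85 | 85/110 = 77.3 | no | out | in | out | out |
| 120 | 82 | 82/120 = 68.3 | no | out | in | out | out |
| 100 | 82 | 82/100 = 82.0 | no | out | in | out | out |
| 100 | 108 | 108/100 = 108.0 | no | out | out | in | out |

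**What follows**

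1. Reading A excludes the swimmer who is exactly at predicted. It does not discriminate.
2. Reading B keeps all three low-ratio swimmers and removes only the one with a high ratio, the reverse of the companion limits. None of the three is caught by the FVC or FEV1 limits.
3. The limit picks out low ratios only under C or D, and both need a word that is not on the page. C and D also disagree with each other about the swimmer at 108%.
4. Supplying the word does not settle the unit. At a predicted ratio of 0.85, an observed 0.805 is below 0.8075 (relative, excluded) but above 0.80 (points, kept).

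**The case against.** The strongest reply is that no one would apply the sentence literally. It sits in a definition of abnormal spirometry, beside two limits for low values, and section 7.0 says that the tests serve to classify normal function. An omitted word is the natural explanation, and trained staff would probably supply it. I accept this as the likely cause. It does not cure the text, because the reader must choose between at least two insertions and two units, and these give different decisions.

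The other screens also count. Section 4.2 separately excludes FEV1 under 80% of predicted, current or treated asthma, exercise-induced asthma and exercise-induced bronchoconstriction, recent tobacco or e-cigarette use, and any positive answer on the first page of the PAR-Q+. Section 4.1 requires self-reported health. These remove some obstruction and narrow the gap, but the airway-disease exclusions depend on a diagnosis or medication, so an undiagnosed low ratio can pass them.

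Three stronger inferences are tempting, and the documents do not support them.

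- *That nobody can be enrolled.* This is what reading A implies, but it cannot be the intention of a plan that says "We plan to recruit up to 30 participants for this project". It shows that the sentence is defective, not what will happen.
- *That the trial does not screen for airflow obstruction.* The defect lies in the ratio limit only; the criteria above remain in force.
- *That the cetirizine comparison is confounded.* Aim 2 is a randomized within-subject crossover. A stable airway abnormality is present under both placebo and cetirizine, so it does not by itself bias the contrast.

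Finally, the spirometry profiles in the tables are assumed. The documents do not show how common they are among these swimmers, or that such a profile would cause desaturation.

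**Conclusion.** The point holds as a drafting error in an operative eligibility rule. Neither literal reading of the ratio limit identifies a low ratio, its inequality opposes the two limits beside it, and the unit of the 5% is missing. That conclusion rests on the text alone. The assumed predicted ratios and profiles only illustrate it.

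The exposed group is limited to swimmers with an undiagnosed low ratio and both FEV1 and FVC at or above 80% of predicted. Their number cannot be estimated from the documents, and nothing shows that any such swimmer was admitted. The consequence is mainly for interpreting Aim 1, where one person can decide the result, and Aim 3, and for the pre-exercise screen. Sample size and analysis model are unaffected, and the Aim 2 contrast is not materially affected. It should be corrected, but it does not undermine the design.

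**What to change.** The sponsor should reconcile the ratio limit in section 4.2 with the FVC and FEV1 limits in the same sentence and with the purpose stated in section 7.0. The revised line should give the intended direction, say whether the margin is relative to the predicted ratio or in percentage points, and state the value. Direction and value are for the sponsor to set; the documents show only that the present wording cannot stand.

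The sponsor should also confirm from the Visit 1 spirometry records that everyone already screened was judged by the intended rule, and record any who were not.

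The cost is one line of text and a check of existing records. FEV1 and FVC are already measured at screening, so no procedure or visit is added and no statistical section changes.

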#### 5.0 Study Design

[figure not shown]

Figure 1: Experimental design for proposed study protocol.

The general study protocol is outlined in Figure 1. For the first testing session, participants will report to the Indiana University Human Performance Laboratory to complete a medical screening and, if willing, consent to the procedures of the study. The medical screening will include measurements of height, weight, resting heart rate, resting blood pressure, and resting pulmonary function along with a health history questionnaire. The second testing session consists of an assessment of risk factors for development of EIAH, specifically changes in blood biomarkers pre- and post-swimming exercise. Participants will report to the Counsilman-Billingsley Aquatics Center and complete an exercise protocol designed to elicit an inflammatory response. Venous blood draws will be performed to assess participants' pre-exercise complete blood count and pre- and post-intense exercise concentrations of plasma IL-1 $\beta$ , IL-8, plasma histamine, whole blood histamine, and histamine release. Measurements of hemoglobin concentration and hematocrit will also be performed pre- and post-exercise in order to correct biomarker

concentrations for fluid loss during exercise. Twelve swimmers (n = 6 men, n = 6 women) will be selected for further trials.

Those selected for further study will visit the Human Performance Laboratory on two occasions separated by at least 48 hours and no more than 60 days. Apart from receiving a placebo (PL) or drug treatment (cetirizine HCl, CH) prior to exercise, participants will perform identical protocols on each visit to the laboratory. Participants will report to the lab and consume either a placebo or CH pill, followed by a health history update questionnaire and their resting pulmonary function will be measured. Participants will then complete a self-selected warm-up that will be standardized across all testing sessions, followed by instrumentation. The exercise protocol beings with a progressive swimming test to maximum aerobic capacity ( $\dot{V}O_{2max}$ ) in a swimming flume, followed by two constant load work bouts at approximately 70 and 85% of the previously recorded HRmax while peripheral capillary oxyhemoglobin saturation (SpO2) is continuously monitored. Participants will receive a 20-min break between each work bout. Drug treatments will be assigned in a double-blind, randomized crossover fashion such that each participant receives each treatment. Concentrations of plasma histamine, whole blood histamine, and histamine release will be assessed from pre- and post-exercise blood samples.

#### 6.0 Enrollment/Randomization

We plan to recruit up to 30 participants for this project to ensure that at least 24 participants will complete the first two visits of the study.

Participants will be recruited from the Indiana University varsity swim team and the associated professional training group. Indiana University is home to a NCAA Division I swim team that is perennially among the nation's top-10 for both men and women. Participants will be recruited from this group of over 50 swimmers using a standard email script.

[figure not shown]
Potential participants will be given the basic information about the study and schedule an appointment for screening if they indicate that they would be interested in participating. Participants will be provided a with detailed description of study procedures prior to study enrollment. Participants will be asked to read the consent form at this time and be encouraged to ask any questions. Participants can then: 1) sign the consent form; 2) take it home for further consideration; or 3) decide not to participate. Participants will be screened once written informed consent has been given.

Experimental trials 3 and 4 will be completed in a double-blinded randomized crossover design. The randomization order will be determined using a customized program (Excel; Microsoft Corporation, Redmond, WA, USA). Subjects will be randomized using the randomization list by order of enrollment in the study by a researcher listed on the IRB personnel. This researcher will also be responsible for drug administration but will otherwise not participate in any data collection or analyses.

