### Table 2: SaO2ear data from Coyle, 2001

A two-way (treatment x intensity) ANOVA using these data produced a Cohen's *f* of 1.22 for the treatment main effect. Therefore, it was determined that using an a priori  $\alpha$  value of 0.05, an estimated twelve subjects are necessary to achieve a power of 0.80. The sample size calculation was conducted using G\*Power 3.1.9.7 (ANOVA: Fixed effects, special, main effects and interactions). Due to the randomized crossover design, all twelve subjects (n = 6 men, n = 6 women) will complete all experimental treatments (PL and CH) at all intensities (70, 85, and 100% of  $\dot{VO}_{2max}$ ).

Previous investigations (Anselme et al., 1994; Mucci et al., 2001) have observed a strong, positive, and significant (r > 0.7; p < 0.05) correlation between  $\Delta$ %H ( $\dot{V}O_{2max}$  - rest) and  $\Delta P_aO_2$  (rest -  $\dot{V}O_{2max}$ ). Using a regression equation ( $\Delta$ %H = 0.0444( $\Delta P_aO_2$ ) - 0.1137; r = 0.80) from Anselme and colleagues (1994), a conservative estimate that a  $\Delta P_aO_2 > 10$  mmHg represents EIAH (Prefaut et al., 2000), we intend to recruit participants for the experimental trials who experience a  $\Delta$ %H > 0.33 during the Selection Exercise Protocol. However, should this inclusion criterion not be met by at least eight subjects, those experiencing the highest  $\Delta$ %H during the Selection Exercise Protocol will be recruited instead.

For proof of principle that EIAH can be prospectively identified using  $\Delta$ %H, a small control group (n=2 men, n=2 women) will also be recruited. For this group, we intend to recruit participants who exhibit the lowest  $\Delta$ %H during the Selection Exercise Protocol. These participants will complete both conditions of the experimental trials.

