### **13.0 Statistical Data Management**

Primary data will be collected via direct data capture from measurement instruments and stored electronically on an electronic spreadsheet on a password protected computer. The storage location will be backed up manually every week. Quality assurance steps will be confirmed by plotting the data prior to formal analyses. Outliers will be identified and checked for authenticity in the database and other original data documents. Extraction and cleaning of data that will be used for analysis will be carried out after each block of subjects used in the randomization of visits 3, 4, and 5 have completed all laboratory visits.

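### The plan does not say whether treatment sequence is assigned before or after the 12 crossover swimmers are selected, or from a balanced list, and the default model has no visit term to absorb an uneven split

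*Combined protocol and SAP*

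**What the plan says.** Section 6.0 states the design, "Experimental trials 3 and 4 will be completed in a double-blinded randomized crossover design", and then the rule for using the list: "Subjects will be randomized using the randomization list by order of enrollment in the study by a researcher listed on the IRB personnel". The order is generated by a custom spreadsheet program. Nothing is said about balance, block size or stratification.

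The same section sets the numbers entering the study: "We plan to recruit up to 30 participants for this project", so that "at least 24 participants will complete the first two visits of the study". It places consent before screening, and so before the Visit 2 test on which selection depends. Section 5.0 then says "Twelve swimmers (n = 6 men, n = 6 women) will be selected for further trials". Section 12.0 makes that selection by the rise in histamine release at Visit 2, and adds that "a small control group (n=2 men, n=2 women) will also be recruited", drawn from the lowest responders.

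The only hint of blocking is in section 13.0, where data are extracted "after each block of subjects used in the randomization of visits 3, 4, and 5 have completed all laboratory visits". The design has no Visit 5.

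For Hypothesis 2, section 12.0 specifies a mixed model with treatment, intensity and their interaction. A visit-order group regressor is added only when a preliminary test shows carry-over.

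**The concern.** A list position taken at enrolment is useful only if the swimmer holding it enters the crossover. If up to 30 swimmers take positions and 12 are kept for reasons unrelated to the list, the 12 are in effect a random draw from it. Any balance built into the list would then not carry over to the crossover.

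In a two-period crossover, equal numbers in the two orders make a visit effect cancel out of the unadjusted treatment difference. The default model here has no visit term, so sequence balance is the only protection. The conditional regressor does not fill the gap. As worded it is for order group, which is a comparison between swimmers; a main effect of that kind does not remove a visit effect from a within-swimmer comparison.

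A visit effect is plausible. The two visits may be up to 60 days apart, so training state can differ. Table 1 shows no graded test, calorimetry or saturation measurement before Visit 3. The documents give no size for such an effect, and none is assumed here.

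**Working it through.** **Plan's own figure.** The documents give no figure for sequence balance. The nearest check is the recruitment target in section 12.0: with X ~ Binomial(26, 0.5), P(X ≥ 8) = 0.986, which agrees with the stated probability above 95%. So 26 is a sound planned list length.

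**Inputs.** Ceiling 30 and at least 24 completing two visits (section 6.0); 26 planned for Visit 2 (section 12.0); 12 in the crossover (section 5.0).

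**Assumptions not in the documents.** For the first four rows of the table: sequences are fixed before selection, the list of length N is balanced N/2 : N/2, and selection is independent of list position.

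**Probability of an uneven split.** If X of the 12 hold the placebo-first order, X ~ Hypergeometric(N, N/2, 12), and P(8:4 or worse) = 1 − P(6) − 2·P(5).

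For N = 30:
- P(6) = C(15,6)² / C(30,12) = 5005² / 86,493,225 = 0.2896
- P(5) = C(15,5)·C(15,7) / C(30,12) = 3003 × 6435 / 86,493,225 = 0.2234
- P(8:4 or worse) = 1 − 0.2896 − 0.4468 = 0.264

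For simple randomisation, X ~ Binomial(12, 0.5): 1 − (924 + 2 × 792)/4096 = 0.388, whether assignment precedes or follows selection.

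| How the list is used | 6:6 | 8:4 or worse | 9:3 or worse |
|---|---|---|---|
| Balanced list of 24, before selection | 31.6% | 22.0% | 3.9% |
| Balanced list of 26, before selection | 30.5% | 23.8% | 4.7% |
| Balanced list of 28, before selection | 29.6% | 25.2% | 5.4% |
| Balanced list of 30, before selection | 29.0% | 26.4% | 6.0% |
| Simple randomisation, any timing | 22.6% | 38.8% | 14.6% |
| Balanced list of 12, after selection | 100% | 0% | 0% |

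**Sensitivity.** With assignment before selection, permuted blocks of 2, 4 or 6 give 22% to 27% for 8:4 or worse. Lists balanced within sex, with six of each sex selected, give 23% to 27%. If the four controls are additional and 16 swimmers enter, 10:6 or worse has probability 19% to 27%.

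**Consequence at 8:4, no visit term.** Let π be the Visit 4 minus Visit 3 effect and τ the drug effect. The drug-minus-placebo difference is τ + π for placebo-first swimmers and τ − π for drug-first swimmers. With 8 in one order and 4 in the other, the average is τ ± π(8 − 4)/12 = τ ± π/3.

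**Consequence at 8:4, visit term fitted.** The variance of the drug estimate is proportional to (1/4)(1/n₁ + 1/n₂). At 6:6 this is 0.0833; at 8:4 it is 0.09375. The ratio is 1.125, so the standard error rises by about 6% (√1.125 = 1.061) and relative efficiency is 1/1.125 = 0.889.

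**The case against.** The strongest reply is that section 6.0 gives an ordering rule, not a time of assignment, and that the context points to the selected swimmers. The paragraph concerns only Visits 3 and 4. In section 5.0 the account of treatment assignment begins from those already selected and says that each participant receives both treatments, which would not be true of swimmers who were never selected. Section 13.0 speaks of randomisation blocks whose members finish every visit; a block holding unselected swimmers could not do so. If the 12 are simply placed on a balanced list in enrolment order, the split is 6:6 and nothing is lost. This stands: a reader might infer from section 6.0 that sequences are fixed before selection and that a balanced list is thereby spoiled, but the documents state neither the timing nor the balance. Figure 1 and the figure in section 6.0 could not be read, so a stated order of steps there cannot be excluded.

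The consequence is also limited. Every swimmer takes both treatments, and over repeated randomisation the estimate is unbiased. Warm-up, diet, abstention and menstrual phase are standardised across visits, and section 7.0 describes the flume as a setting such swimmers already train in. These points reduce a visit effect but do not remove it: the metabolic snorkel, the first instrumented maximal test and changes in training state remain.

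A reader might also infer that, because the four controls could all receive one order, drug and visit would be inseparable in that group. No treatment comparison within controls is planned. They serve the proof of principle and the pooled correlation, so this reading has no consequence for the plan.

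**Conclusion.** The point holds as a gap in specification, not as a demonstrated flaw. The plan leaves open when sequence is assigned and whether the list is balanced. The chance of 8:4 or worse is 22% to 26% if a balanced list of 24 to 30 is used before selection, about 39% under simple randomisation at any time, and zero if a balanced list is applied to the selected 12. The first range rests on the literal reading of the enrolment rule and on selection being independent of list position.

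It would go too far to call the crossover broken or the drug estimate systematically biased. What is at stake is that, in an unlucky allocation, one third of a visit effect of unknown size enters the analysis of a primary aim with 12 swimmers, and the default model has nothing to remove it. The correction is worth making because it costs almost nothing.

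**What to change.** In section 6.0, state that sequence is assigned after Visit 2 selection, in order of entry to Visit 3, from an explicitly balanced list: 6:6 overall and 3:3 within each sex. Balance has to be stated, because moving the assignment alone does not help a simple list.

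In section 12.0, include visit (period) as a fixed effect in the Hypothesis 2 model, whatever the carry-over test shows.

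Reconcile two related passages. First, say whether the four controls are inside the 12, as the pooled n of 12 for Hypothesis 3 implies, or additional to them. If additional, 16 swimmers enter (6 + 2 = 8 of each sex) and the list becomes 8:8 overall and 4:4 within sex. Balance within the high-release and control groups is optional and depends on that answer. Second, correct the reference to Visit 5 in section 13.0 and the matching visit range in the screening paragraph of section 7.0.

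The cost is a sentence in each of sections 6.0 and 12.0, a regenerated spreadsheet list, and one degree of freedom for the visit term (in a simple paired analysis of 12, from 11 to 10). The researcher who already handles randomisation and drug administration can hold the list. No swimmers, visits or staff are added.
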